Almost all patients had clear cell histology (60 of 64 patients) and they had all been nephrectomised.

There were 26 patients with a single metastasis site versus 23 who had 2 affected organs and 15 patients who had 3 or more sites.

The median time to eliminate all lesions from the beginning of exclusive treatment with TKI was 12.6 months, with a range of 2 to 28 months. The median time from CR to relapse was 7.9 months.

In the subjects in whom remission of the lesions with the TKI plus the local treatment was achieved, 18.5 months were needed (range of 5-45 months)

The median time from CR to relapse was 8.2 months.

The decision to interrupt treatment or not was as follows:

[figure not shown]

Fig 2. Outcome of patients who achieved complete remission (CR) with a tyrosine kinase inhibitor (TKI) alone.

The author's conclusion was that CR can be obtained in all prognostic groups and with metastases at any site.

In the retrospective analysis of the registry of the Czech renal cancer cooperative group (Buchler et al., 2016) (RENIS registry) covering 95% of patients treated outside clinical trials, of 2803 patients, 100 cases of CR were identified as best response (3.6% of the total) obtained exclusively with a TKI in first line:

- 84 patients treated with Sunitinib
- 4 patients treated with Pazopanib
- 9 with Sorafenib
- 3 with Bevacizumab + Interferon alpha

96% of the patients had been nephrectomized and the same percentage of tumours were clear cell histology.

Regarding the MSKCC classification of the prognosis group, 47% of the patients had a good prognosis, while 51% had been classified as intermediate prognosis and the prognosis was poor in 2%.

The response was analysed according to RECIST 1.1 criteria, and only one image was needed to confirm the CR.

The median time to reach CR was 10.1 months, and the number of patients with CR increased linearly up to approximately 20 months after the start of treatment with the anti-angiogenic drug.

The patients had a median PFS of 3.8 years (45.6 months) and OS had not been reached in this cohort. 5-year survival was 80%.

The decision to continue the treatment or not once the lesions disappeared was shared by the clinician and the patient.

Patients who reached CR very quickly (before 10 months) were more likely to continue treatment, while a greater proportion of those in whom the lesions disappeared later decided to discontinue treatment.

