2.1 STUDY DESIGN

Observational, retrospective, multicentre study in spanish patients with metastatic Renal Cell Carcinoma (mRCC) treated with sunitinib as a first-line treatment (treatment with previous cytokine therapy is accepted) according to clinical practice who obtained a complete response (CR) to treatment in one of these 2 situations:

- a) Complete response (CR) obtained exclusively with first-line sunitinib treatment (sunitinib CR).*
- b) Response obtained after a period of time on treatment with sunitinib in which local treatment was also performed (surgery of the residual metastasis/metastases, radiofrequency ablation or radiotherapy) to achieve the total macroscopic disappearance of the disease, according to the opinion of the physician responsible for the patient (CR + local treatment).*

The patient population eligible for this study includes any patient with advanced or metastatic renal cancer treated with Sunitinib and who has achieved a CR to the tumour and its metastases at some point in the treatment and according to the usual evaluation criteria in daily clinical practice irrespective of whether it was obtained with Sunitinib alone or local treatment was required to eradicate all lesions: (residual metastasis(es), radiofrequency ablation or radiotherapy)

The requirements for a patient's inclusion are that:

- 1. These patients must have Sunitinib as first-line treatment in accordance with its Summary of Product Characteristics.*
- 2. Collection of clinical, safety and response data in patients with advanced kidney cancer.*

The study is expected to be conducted in at least 50 sites throughout Spain in order to reach the maximum number of study patients.

Case collection will start at each site after the contract with the site has been signed, all the study documentation is available and training in the procedures and objectives of the protocol has been provided by the person appointed by the sponsor.

Any number of patients that meet the inclusion criteria and no exclusion criteria may be recruited at the site.

This is an observational study designed to reflect routine clinical practice; there will be no interference with the daily routine of the medical care provided to kidney cancer patients.

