4.1.1. Inclusion Criteria

Patients must meet all the inclusion criteria below to be eligible for inclusion in the study:

[figure not shown]
1. Patients aged 18 years or older who have been treated for a metastatic renal carcinoma with first-line sunitinib in (prior cytokine treatment is admitted) between 2007 and October 30, 2018 and have obtained, as best response to treatment, total disease remission in the opinion of the treating physician from the clinical, radiological and/or macroscopic standpoint. This response must have been achieved through two possible strategies:
 - a. Systemic treatment with Sunitinib alone.
 - b. Treatment with Sunitinib and subsequent local treatment for one or several residual lesions that have not responded to the drug (traditional surgery, radiotherapy, SBRT (Stereotactic Body Radiation Therapy)).
2. The duration of the CR must have been confirmed by at least 2 consecutive imaging tests with no limit on the duration of this response. Patients with subsequent progression may be included in this registry.
3. Patients of any risk group.
4. Tumours of any histology.

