4.4 SUBGROUPS

NA

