5.1 EFFICACY/EFFECTIVENESS OBJECTIVES

Efficacy is assessed by describing the complete responses in daily clinical practice in Spain in patients with metastatic renal carcinoma treated with first-line Sunitinib, defined as the documented disappearance of all lesions in the investigator's opinion in at least 2 consecutive CT scans. The treatment may be with Sunitinib alone (CR Suni) or Sunitinib plus a local treatment to eliminate residual disease (CR + local treatment).

The baseline characteristics of both patient and tumour will be described to seek predictive response factors. The following variables will be considered:

- Demographic characteristics (age at the start of treatment)
- Comorbidities: cardiac, renal, endocrine, autoimmune and hepatic.
- Previous nephrectomy
- Classification of the risk group according to Motzer and/or Heng criteria and of the association between each one of the prognostic variables, such as: patient baseline status, time elapsed from nephrectomy to the start of systemic treatment, presence of anaemia, corrected calcium, LDH levels, neutrophil and platelet levels.
- Tumour data: histology, Fuhrman grade, presence of tumour necrosis and number and location of metastases (organs involved).

Secondary efficacy objectives evaluated will be time on treatment with Sunitinib until CR, duration of complete response and the time elapsed from CR to disease stabilisation/progression or change of treatment due to unacceptable toxicity or death from any cause.

The subjects with the greatest clinical benefit will be evaluated on the basis of the therapeutic strategy adopted in order to develop recommendations to be followed in patients who obtain CR. Moreover, the decision to discontinue treatment after a period of maintenance of CR and the pharmacological group by the mechanism of action used in second line after disease the progression will be evaluated.

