7.2.4. Efficacy analysis

Depending on the **primary objective of the study**, the complete responses (CR) observed in Spanish daily clinical practice in patients with advanced carcinoma with a renal cell component that have received first-line treatment with Sunitinib will be described. All demographic and clinical characteristics will be summarised descriptively.

More specifically, the following baseline features of both patient and tumour will be described:

- Demographic characteristics (age at the start of treatment of the metastatic disease).
- Comorbidities: presence of cardiovascular, hepatic, renal, autoimmune, chronic dermatological, obesity and/or intestinal disease.
- Tumour data: number and site of metastases, tumour histology, Fuhrman grade and presence of tumour necrosis.
- Previous nephrectomy in the treatment of metastatic renal cancer and time elapsed from nephrectomy to the start of systemic treatment.
- Classification of the risk group according to Motzer and/or Heng criteria.
- Patient's baseline status, including ECOG grade, presence of anaemia, corrected calcium, LDH levels, neutrophil and platelet levels.

Central tendency measures (mean and median) and dispersion measures (standard deviation and interquartile range) will be used for the quantitative variables. Frequency distributions (absolute and relative) will be presented for categorical data. Bivariate comparisons between baseline characteristics and events of interest of a continuous nature will be made by parametric tests (Student's t test, one-way ANOVA) or their non-parametric equivalents (Mann-Whitney, Kruskal-Wallis) depending on the distribution of the variables. In the case of categorical variables, the Chi-squared test or Fisher's exact

PFIZER CONFIDENTIAL

test, as applicable, will be used for the comparison of frequency distribution.

The **secondary outcome measures** pertaining to the follow-up time until the event of interest (complete disease remission, disease progression, change of treatment due to unacceptable toxicity or death from any cause) will be described by estimating survival functions using the Kaplan-Meier method. Specific estimates and 95% confidence intervals will be provided for the median, 25th percentile and 75th percentile of the distributions of each secondary variable. The secondary outcome variables related to follow-up time are:

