- Time on treatment with Sunitinib until complete remission of lesions, calculated as the difference between treatment start date and CR confirmation date (2nd CT scan).
- Duration of complete remission (DOR)
- Progression-free survival (PFS) or time from remission to disease progression, change of treatment due to unacceptable toxicity or death. It will be calculated as the time elapsed from the RC confirmation date (2nd CT scan) until the date of progression/death or change of treatment for unacceptable toxicity, as applicable, or else it will be censored on the date of the last patient follow-up.

Taking into account the asymmetry normally observed in the distribution of survival times and that follow-up periods may be uneven (different study entry date), the Kaplan-Meier method will be used to estimate the median time to CR together with its 95% confidence interval. The median will indicate when complete remission of the disease occurred in 50% of patients.

In order to find associations between time to CR and the baseline features of both patient and tumour, a log-rank test will be used for comparison between groups and the determination of the statistical significance of the correlation between each of the baseline variables and the time to complete remission of disease. The following baseline characteristics are considered:

[figure not shown]
- Demographic characteristics
- Comorbidities
- Tumour data
- Prior nephrectomy in the treatment of metastatic renal cancer
- Classification of the risk group according to Motzer and/or Heng criteria.
- Patient's baseline status, including ECOG grade, presence of anaemia, corrected calcium, LDH levels, neutrophil and platelet levels.

This analysis will establish which baseline characteristics are associated with a shorter complete response time to treatment.

As part of the secondary objectives, the doses and treatment regimens observed in the sample will also be descriptively summarised by means of absolute and relative frequencies. In the case of changes in the treatment dose, the frequency of patients with dose increase, dose reduction and changes in the rest regimen will be specified. Similarly, the most frequent reasons for changes in dosage and/or treatment regimen to RC will be reported.

Frequencies of the type of treatment received will be presented, depending on whether it

Pfizer Confidential

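### The SAP commits to only one pooled median time to CR for two pre-defined routes; it should add the median by route

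*SAP*

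**What the plan says.** SAP 4.1.1 admits patients in CR and adds: "This response must have been achieved through two possible strategies". The two strategies are sunitinib alone, and sunitinib followed by local treatment of residual lesions that the drug had not cleared. SAP 2.1 and 5.1 name the same two categories.

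The planned time-to-event summaries do not use them as groups:

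- The section headed "4.4 SUBGROUPS" contains only the entry NA.
- SAP 7.2.4 says of the secondary time variables: "Specific estimates and 95% confidence intervals will be provided for the median, 25th percentile and 75th percentile of the distributions of each secondary variable". No split by route is given.
- For time to CR, "the Kaplan-Meier method will be used to estimate the median time to CR together with its 95% confidence interval", and the result is read as follows: "The median will indicate when complete remission of the disease occurred in 50% of patients".
- The log-rank comparisons of time to CR list baseline patient and tumour features only.

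Route does appear elsewhere in SAP 7.2.4. Treatment type is tabulated by frequency. The local-treatment group is described by technique, timing, histology, necrosis and surgical complications. Type of treatment received is also among the covariates for a multivariate Cox regression on CR/PFS, provided that proportional hazards holds. Protocol 8.7 allows a stratified analysis as an option and names no stratum.

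**The concern.** Time to CR does not measure the same thing in the two routes. With sunitinib alone, it is the time the drug takes to clear all lesions. With local treatment, the first lesion-free scan cannot come before the procedure, so the interval also reflects when the team chose to operate or irradiate. This is so whether the interval ends at the first clear CT scan (SAP 5) or at the confirming scan (SAP 7.2.4).

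The median time on sunitinib until remission is a secondary objective (Protocol 7.2, SAP 2.2), and the results are meant to support treatment recommendations. If the routes differ, a clinician who reads one pooled median as the time a patient on sunitinib alone needs, or as the time a patient who also had local treatment needs, will be misled. Two registries with identical results within each route could also report different pooled medians simply because their mix of routes differed.

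**Working it through.** The plan gives no figure to reproduce. Protocol 8.5 makes no sample size calculation and treats 90 patients as an estimate. The check is therefore an illustration built on the one series in the documents that reports both routes (Protocol 6, SAP 2).

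**Inputs**

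- Patients: 36 drug only and 28 with local treatment; 36 + 28 = 64, as stated. The drug-only share is w = 36/64 = 0.5625.
- Time to CR: a median of 12.6 months (range 2 to 28) for drug only. For the local-treatment route the text says "18.5 months were needed (range of 5-45 months" without calling the figure a median; it is treated as one here.
- Time from CR to relapse: medians of 7.9 months (drug only) and 8.2 months (with local treatment).
- Assumed shapes: exponential, Weibull with shape 2, and lognormal with log-SD 0.5 and 0.7.

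**Pooled median.** Solve w·F1(t) + (1 − w)·F2(t) = 0.5, where F1 and F2 are the distribution functions for the drug-only and local-treatment routes.

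Worked for the exponential case at t = 14.82:

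- F1 = 1 − 0.5^(14.82/12.6) = 0.557
- F2 = 1 − 0.5^(14.82/18.5) = 0.426
- 0.5625 × 0.557 + 0.4375 × 0.426 = 0.313 + 0.186 ≈ 0.50

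Time to CR at w = 0.5625:

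| Assumed shape | Pooled median (months) | Drug-only patients in CR by then | Local-treatment patients in CR by then |
|---|---|---|---|
| Exponential | 14.8 | 56% | 43% |
| Weibull, shape 2 | 14.7 | 61% | 36% |
| Lognormal, log-SD 0.5 | 14.9 | 63% | 33% |
| Lognormal, log-SD 0.7 | 14.9 | 60% | 38% |

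The pooled value lies 2.1 to 2.3 months above 12.6 and 3.6 to 3.8 months below 18.5.

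**Dependence on case mix** (within-route distributions held fixed):

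| Drug-only share | Pooled median time to CR (months) |
|---|---|
| 25% | 16.7 to 16.9 |
| 50% | 15.1 to 15.3 |
| 75% | 13.7 to 13.8 |
| 90% | 13.0 to 13.1 |

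**CR duration.** The same calculation with 7.9 and 8.2 months gives 8.03 months at w = 0.5625, and 8.12 to 7.93 months as the drug-only share goes from 25% to 90%. Pooling makes no material difference on these figures.

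**Precision if split.** Ninety patients at 36:28 give 90 × 36/64 = 50.6 and 90 × 28/64 = 39.4, so about 51 and 39. For lognormal times the approximate 95% interval is median × exp(±1.96 × 1.253 × log-SD/√n).

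| Log-SD | Drug only, n = 51 | With local treatment, n = 39 |
|---|---|---|
| 0.5 | 10.6 to 15.0 months | 15.2 to 22.5 months |
| 0.7 | 9.9 to 16.0 months | 14.0 to 24.4 months |

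**The case against.** The strongest reply is that the pooled median answers the question asked. The target population is everyone in CR by either route, and the objective of median time to remission carries no restriction by route. This stands. A reader might infer that the pooled median is biased, too long for one route and too short for the other. The documents do not support that, because it is a correct summary of a mixed population. What is missing is the by-route figure beside it.

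A second reply is that route is not ignored. This also stands in part. The Cox model includes it, and the timing of local treatment is already to be described. But the model depends on proportional hazards, has no stated fallback and yields a hazard ratio rather than a median. The stratification in Protocol 8.7 is optional and depends on the results.

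A reader might also infer that baseline features linked to selection for local treatment will pass for predictors of slow response. That could happen in the log-rank tests, which are not adjusted for route. The planned Cox model adjusts for it, so the inference is too strong. Stratifying those tests by route is not the answer. Route is decided after baseline, partly by which lesions failed to respond, so stratifying would condition on response. A stratified Cox model would also remove the route hazard ratio that the SAP intends to estimate.

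Finally, the illustration rests on one series in which 5 of 64 patients took sorafenib, and the time-to-CR ranges overlap. That limits its weight as a forecast for this registry.

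**Conclusion.** The concern holds for time to CR, as a cheap improvement to the plan. Two routes are defined in advance, the endpoint means something different in each, and no by-route median is committed to. On the cited figures the pooled median would be about 14.7 to 14.9 months against 12.6 and 18.5, and would move between about 13.0 and 16.9 months with case mix alone. This assumes the cited medians and mix, 18.5 months being a median, and the distributions listed; none of it is a result for this registry.

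A reader might extend the point to CR duration. The only by-route figures in the documents, 7.9 and 8.2 months, show no material difference. They measure time to relapse, whereas the SAP's duration of response also ends at a treatment change for toxicity or at death. A larger gap in this registry is possible but not shown.

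**What to change.** 1. In SAP 4.4, replace NA with the two routes: sunitinib alone, and sunitinib plus local treatment.
2. In SAP 7.2.4, add the Kaplan-Meier median time to CR by route with its 95% confidence interval, alongside the pooled estimate, and state that the pooled value depends on the mix of routes.
3. Report duration of response and PFS from CR by route for completeness.
4. For the local-treatment route, summarise time from the start of sunitinib to the local procedure. This sharpens the timing description already planned.
5. Keep route as a Cox covariate. Do not stratify the baseline-predictor tests by route.

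The cost is a few more tables and wider intervals within each route, with about 51 and 39 patients if 90 are enrolled at the cited mix. Treatment type and the timing of local treatment are already to be recorded, so no new data are needed.

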7.2.2. Descriptive analysis

The mean value, standard deviation, median, minimum, maximum, interquartile range (RIQ) and 95% confidence interval (CI 95%) of the following variables will be provided:

- Age of the patients at the start of treatment.
- Pre-treatment necrosis percentage

PFIZER CONFIDENTIAL

[figure not shown]

- Laboratory data at the start of treatment:
 - Haemoglobin
 - Leukocytes
 - Corrected calcium
 - LDH levels
 - Lymphocytes
 - Platelets
 - Neutrophil/Lymphocyte rate
- Time elapsed from the nephrectomy to the start of systemic treatment
- Time on treatment until CR is reached
- Duration of CR
- Time on treatment after CR is reached

The frequency distribution of patients will be presented according to:

[figure not shown]
- ECOG:
 - 0
 - 1
 - 2
 - 3
 - 4
- KPS (Karnofsky Performance Status):
 - 0%
 - 10%
 - 20%
 - 30%
 - 40%
 - 50%
 - 60%
 - 70%
 - 80%
 - 90%
 - 100%
- Motzer prognostic criteria:
 - Favourable (0 factors)
 - Intermediate (1-2 factors)
 - Poor (3 or more factors)
- Heng prognostic criteria:
 - Favourable (0 factors)
 - Intermediate (1-2 factors)
 - Poor (3 or more factors)
- Comorbidities:

PFIZER CONFIDENTIAL

- Cerebrovascular disease
 - Liver disorders
 - Renal failure
 - Autoimmune disease
 - Chronic dermatological disease
 - Obesity
 - Bowel disease
- Metastasis site:
 - Lung
 - Liver
 - Brain
 - Pancreas
 - Nodes
 - Other
- Fuhrman grade:
 - I
 - II
 - III
 - IV
- TNM tumour stage
- Histological type:
 - Clear cell
 - Chromophobe
 - Sarcomatoid, percentage
 - <20%
 - 20-30%
 - 31-50%
 - 51-75%
 - >75%
 - Papillary type 1
 - Papillary type 2
 - Mixed
 - Not performed
- Previous nephrectomy:
 - Yes
 - No
- Complications during surgery:
 - Yes
 - No
- Initial dose and treatment regimen:

PFIZER CONFIDENTIAL

- Sunitinib 50 mg 4/2 regimen
- Sunitinib 50 mg 2/1 regimen
- Sunitinib 37.5 mg 4/2 regimen
- Sunitinib 37.5 mg 2/1 regimen
- Sunitinib 25 mg 4/2 regimen
- Sunitinib 25 mg 2/1 regimen

- Type of treatment received:

- Sunitinib monotherapy
- Sunitinib + subsequent local treatment
- Local treatment techniques for residual lesions:
 - Traditional surgery
 - Radiotherapy
 - SBRT

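### The univariable test of every baseline variable against time to CR is a between-group log-rank test, but age, calcium, LDH, neutrophils, platelets and metastasis count are values or counts with no grouping fixed

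*SAP*

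**What the plan says.** SAP 7.2.4 (Efficacy analysis) names one univariable test for time to CR: "a log-rank test will be used for comparison between groups and the determination of the statistical significance of the correlation". The test is applied to every baseline variable, with time to CR as the outcome. The list of variables that follows includes demographic characteristics, tumour data and "Patient's baseline status, including ECOG grade, presence of anaemia, corrected calcium, LDH levels, neutrophil and platelet levels". Earlier in the same section the first two headings are spelled out: "Demographic characteristics (age at the start of treatment of the metastatic disease") and "Tumour data: number and site of metastases, tumour histology, Fuhrman grade and presence of tumour necrosis". Age and number of metastases are therefore in scope.

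SAP 5 collects age, the laboratory data and the number of metastases as values or counts. SAP 7.2.2 summarises "Age of the patients at the start of treatment", corrected calcium, LDH and platelets as continuous: "The mean value, standard deviation, median, minimum, maximum, interquartile range (RIQ) and 95% confidence interval (CI 95%) of the following variables will be provided". That list has the neutrophil/lymphocyte ratio but not the neutrophil count alone, and it does not include the number of metastases.

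Protocol 8.3 (Variables) leaves full variable definitions to the SAP. The covariate table in SAP 5.4 assigns calcium, LDH and platelets to a risk-group category, gives age simply as age, and places number of metastases under disease data. It contains no cut-off and no number of groups.

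Two other parts of the plan bear on the point. The Heng and Motzer entries in the protocol's list of abbreviations name hypercalcaemia, neutrophilia, thrombocytosis and raised LDH as present/absent factors, without numeric limits. SAP 7.2.4 also plans a multivariate Cox regression, provided that proportional hazards hold, and does not say how covariates are coded.

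**The concern.** A log-rank test compares groups. It cannot be run on an LDH value or an age until someone has grouped the patients, and the plan leaves open how, and when, that is done. Two things can follow. Any fixed grouping discards the ordering within groups, so a real gradient is harder to detect. And if the grouping is settled after the curves have been seen, the nominal 5% level no longer applies.

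SAP 7.2.4 says that this analysis will establish which baseline characteristics go with a faster response. The same section says that its results will feed recommendations on therapeutic strategy. About 90 patients are expected, so there is little information to spare, and cut-offs tuned to this series would not carry over to another.

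**Working it through.** **Inputs from the documents.** About 90 cases (SAP 4.1). CR is an inclusion criterion (SAP 4.1.1), so all of them count as events for time to CR: D = 90, no censoring. Significance level 0.05 (SAP 3.2); sidedness is not stated and two-sided is assumed. The documents give no power, effect size or sample-size basis (Protocol 8.5), so there is no planned figure to reproduce.

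**Assumptions.** A roughly normal covariate with a linear effect on the log hazard. Hazard ratio 1.35 per SD as the working value, with a range of 1.2 to 1.5.

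**Step 1: information kept after grouping.** For a two-way split with share p on one side, the retained fraction is φ(z_p)² / [p(1 − p)].

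- Median split: 0.3989² / 0.25 = 0.637, a loss of 36%.
- 25/75 split: retained 0.539, loss 46%.
- 20/80 split: retained 0.490, loss 51%.
- 10/90 split: retained 0.342, loss 66%.

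For k equal groups the retained fraction is the between-group share of variance: tertiles 0.793, quartiles 0.861, quintiles 0.897 (losses of 21%, 14% and 10%). Shape matters too: a median split loses 25% for a uniform covariate and 52% for an exponential one.

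**Step 2: power with 90 events at a hazard ratio of 1.35 per SD.** ln 1.35 = 0.300.

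- Continuous: √90 × 0.300 − 1.96 = 2.847 − 1.96 = 0.887, power 81%.
- Median split: the log hazard ratio between halves is 0.300 × 4φ(0) = 0.300 × 1.596 = 0.479. Then √(90 × 0.25) × 0.479 − 1.96 = 2.272 − 1.96 = 0.312, power 62%.
- 20/80 split: √(90 × 0.300² × 0.490) − 1.96 = 0.03, power 51%.
- Tertiles (2 df) 62% and quartiles (3 df) 59%, from the noncentral chi-square. More groups keep more information, but the extra degrees of freedom use up the gain.

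Simulation of exponential times with n = 90 gives slightly lower values: 77% continuous and 57-58% for the median split.

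| HR per SD (assumed) | Continuous | Median split |
|---|---|---|
| 1.2 | 41% | 28% |
| 1.3 | 70% | 51% |
| 1.35 | 81% | 62% |
| 1.4 | 89% | 72% |
| 1.5 | 97% | 87% |

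In terms of events, 80% power needs (1.96 + 0.842)² / (ln HR)². At a hazard ratio of 1.345 per SD this is 7.85 / 0.0878, or 90 events. With a median split it is 7.85 / (0.0878 × 0.637), or 141 events.

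**Step 3: false positives if the cut-off is chosen from the data.** Simulation with no true effect, n = 90, 10,000 runs, rejection at |z| > 1.96:

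- continuous value: 5.3%
- median split fixed in advance: 5.3%
- best of five quantile cut-offs: 17.8%
- best cut-off anywhere between the 20th and 80th percentile: 32.7%

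A grouping fixed beforehand costs power but keeps the error rate. Only a searched cut-off inflates it.

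**The case against.** The strongest reply is that the log-rank test is not the whole association analysis. SAP 7.2.4 goes on to a multivariate Cox model that reports hazard ratios for time to complete remission and could take these variables as continuous. This stands in part: the loss applies mainly to the univariable step. But the Cox model is conditional on proportional hazards, leaves its coding open, and does not replace the univariable test that the SAP relies on to say which characteristics are associated with faster response.

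Second, calcium, LDH, neutrophils and platelets enter the plan as components of the Motzer and Heng scores, and the log-rank list places them next to anaemia as present or absent. Reading them as clinical risk-factor groups is natural, and such groups would transfer to other series. This also stands in part. No numeric limits are given, the test is not tied to those factors, and the list calls these variables levels. Age and number of metastases have no grouping at all.

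Third, SAP 7.2.4 also plans t-tests, ANOVA or rank tests for outcomes of a continuous nature. These too compare groups, so they do not supply an analysis of a numeric baseline variable on its own scale.

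A reader might infer that the plan discards about a third of the information, or that it carries a false-positive rate near 30%. The documents support neither. The first figure belongs to a median split of a near-normal variable, which the SAP does not propose. The second describes a cut-off search that the SAP does not describe; it shows what the missing rule permits.

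Finally, the study is descriptive and has no hypothesis. That limits the weight of the point but does not remove it, because the SAP still sets a significance level and draws conclusions from these tests.

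**Conclusion.** The point holds for the univariable analysis of numeric baseline variables. The stated test forces a grouping that neither document defines, least of all for age and number of metastases.

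The size depends on the unstated grouping. The loss of information is about 36% for a median split and roughly 10% to 66% for other groupings of a normal variable. At an assumed hazard ratio of 1.35 per SD with 90 events, power is about 77-81% continuous against 57-62% with a median split; over 1.2 to 1.5 it is 41-97% against 28-87%. If cut-offs were chosen from the data, the error rate for one null variable could be about 18-33%. These figures assume a linear log-hazard effect, about 90 events without censoring, and a two-sided 5% level.

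The documents do not support the broader conclusion that the whole search for predictors is compromised, since the Cox model may recover the continuous information if it is coded that way. The change is worth making before analysis, because a better method from a model class already in the plan can use data already collected.

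**What to change.** In SAP 7.2.4:

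- For age, corrected calcium, LDH, neutrophils, platelets and number of metastases, replace the log-rank test by univariable Cox regression on the continuous value or count, on the log scale where skewed. Report the hazard ratio with its 95% confidence interval and a check of linearity, for example with a spline.
- Use the same coding in the multivariate Cox model, and state it.
- Keep the log-rank test for categorical factors, and for Heng and Motzer factors whose numeric limits are written into the SAP before database lock.
- State that no cut-off will be chosen from these data.

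The cost is SAP wording, slightly more analysis work, and reliance on a linearity assumption that must be checked. No new data are needed.
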